## **5.4.1.2** Safety Endpoints

A primary objective of this trial is to characterize the safety and tolerability of navarixin in participants with advanced/ metastatic solid tumors when administered in combination with pembrolizumab. The primary safety analysis will be based on participants who experience toxicities as defined by CTCAE Version 4.0.3 criteria. Safety will be assessed by quantifying the toxicities and grades of toxicities experienced by participants who have received navarixin in combination with pembrolizumab.

Safety parameters commonly used for evaluating investigational systemic anti-cancer treatments are included as safety endpoints for the study including, but not limited to, the incidence of, causality to, and outcome of AEs/SAEs; changes in vital signs and laboratory values. Adverse events will be assessed as defined by CTCAE, Version 4.0.3.

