## 9.3.1 Time Period and Frequency for Collecting AE, SAE and Other Reportable **Safety Event Information**

All AEs, SAEs and other reportable safety events that occur after the consent form is signed but before treatment allocation/randomization must be reported by the investigator if the participant is receiving placebo run-in or other run-in treatment, if the event cause the participant to be excluded from the study, or is the result of a protocol-specified intervention, including but not limited to washout or discontinuation of usual therapy, diet, or a procedure.

- All AEs from the time of treatment allocation/randomization through 30 days following cessation of study treatment must be reported by the investigator.
- All AEs meeting serious criteria, from the time of treatment allocation/randomization through 90 days following cessation of study treatment, or 30 days following cessation of study treatment if the participant initiates new anticancer therapy. whichever is earlier must be reported by the investigator.
- All pregnancies and exposure during breastfeeding, from the time of treatment allocation/randomization through 120 days following cessation of study treatment, or 30 days following cessation of study treatment if the participant initiates new anticancer therapy must be reported by the investigator.
- Additionally, any SAE brought to the attention of an investigator at any time outside of the time period specified above must be reported immediately to the Sponsor if the event is considered to be drug-related.

Investigators are not obligated to actively seek AE or SAE or other reportable safety events in former study participants. However, if the investigator learns of any SAE, including a death, at any time after a participant has been discharged from the study, and he/she considers the event to be reasonably related to the study treatment or study participation, the investigator must promptly notify the sponsor.

All initial and follow-up AEs, SAEs and other reportable safety events will be recorded and reported to the sponsor or designee within the timeframes as indicated in Table 7.

Reporting Time Periods and Timeframes for Adverse Events and Other Reportable Safety Events

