### 10.4.2 Safety Endpoints

The primary safety endpoint is the number/proportion of participants with DLTs (including participants with Grade 4 ANC decrease), and AEs, and who discontinue study treatment due to AEs. In addition, safety and tolerability will be assessed by clinical review of all relevant parameters including adverse events (AEs), laboratory tests, and vital signs.

A description of safety measures is provided in Section 9.5 - Safety.

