### **10.6.2** Statistical Methods for Safety Analysis

Safety and tolerability will be assessed by clinical review of all relevant parameters including DLTs, AEs, SAEs, laboratory tests, vital signs, ECG measurements, and physical examinations

DLT and adverse events will be summarized by counts and frequencies for each arm. Laboratory tests, vital signs, and other safety endpoints will be summarized as appropriate (e.g., counts, percentages).

Miettinen and Nurminen's method will be used to estimate the difference between the 2 arms and its 95% confidence interval for number of participants with a DLT, number of participants with ≥1 AE and number of participants discontinuing study treatment due to an AE.

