## 12.4 Appendix 4: Adverse Events: Definitions and Procedures for Recording, Evaluating, Follow-up, and Reporting

#### **Definition of AE**

#### **AE Definition**

- An AE is any untoward medical occurrence in a patient or clinical study participant, temporally associated with the use of study treatment, whether or not considered related to the study treatment.
- NOTE: An AE can therefore be any unfavorable and unintended sign (including an abnormal laboratory finding), symptom, or disease (new or exacerbated) temporally associated with the use of a study treatment.
- NOTE: for purposes of AE definition, study treatment (also referred to as Sponsor's product) includes any pharmaceutical product, biological product, vaccine, device, diagnostic agent or protocol specified procedure whether investigational (including placebo or active comparator product) or marketed, manufactured by, licensed by, provided by or distributed by the sponsor for human use in this study.

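### The only adverse-event contrast between doses is any grade and any cause; no between-arm safety contrast uses grade after Cycle 1

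*Combined protocol and SAP*

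**What the plan says.** Section 10.6.2, repeated in the Section 10.1 summary, states that "Miettinen and Nurminen's method will be used to estimate the difference between the 2 arms and its 95% confidence interval" for three items: the "number of participants with a DLT" and the "number of participants with ≥1 AE and number of participants discontinuing study treatment due to an AE". Section 10.4.2 makes the same three items the primary safety endpoint: "The primary safety endpoint is the number/proportion of participants with DLTs (including participants with Grade 4 ANC decrease), and AEs, and who discontinue" treatment because of AEs.

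The AE item carries no limit on grade, seriousness or relatedness. Appendix 4 counts an event as an AE "whether or not considered related to the study treatment". On the collection window, Section 9.3.1 says: "All AEs from the time of treatment allocation/randomization through 30 days following cessation of study treatment must be reported by the investigator". Treatment may last up to 35 administrations, about two years.

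Section 5.4.1.2 sets a different emphasis: "Safety will be assessed by quantifying the toxicities and grades of toxicities experienced by participants". Section 10.6.2 also plans counts and frequencies of DLTs and AEs per arm, and clinical review of SAEs, laboratory tests and other parameters. It lists no between-arm difference by grade or relatedness.

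**The concern.** Section 5.4.1.2 promises an assessment by grade, but the one AE contrast ignores grade. An any-grade, any-cause count collected over a long window in advanced cancer may approach 100% in both arms. The documents point that way. Worsening laboratory values can count as AEs (Appendix 4). Hematology and chemistry are drawn every cycle (Section 2). Navarixin itself lowers ANC, by a median of 24% at 30 mg and 48% at 100 mg (Section 3.2.1.1).

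Near the ceiling, the estimated difference is forced towards zero and its interval is narrow. A reader could take that as evidence that the doses are equally tolerable, even when severe toxicity differs. Only two doses are randomized, so their relative tolerability is one of the more useful results the trial can give.

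**Working it through.** **Inputs from the documents.** Method and level: Miettinen-Nurminen, 95% (10.6.2). Allocation 1:1 (7.3). Size: 60 per arm at full enrolment (10.9), or as few as 60 in total, so 60/2 = 30 per arm (5.2). The plan gives no expected AE rate and no precision for any safety contrast, so there is no stated figure to reproduce. All event rates below are my assumptions.

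**Method.** With n per arm and counts xB (100 mg) and xA (30 mg), the Miettinen-Nurminen interval excludes zero when |z| > 1.96, where

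z = (xB/n − xA/n) / sqrt[ p(1−p) × (2/n) × 2n/(2n−1) ], and p = (xA + xB)/(2n).

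The probability of excluding zero is the sum of the two binomial probabilities over all pairs of counts that meet this condition. The plan estimates and does not test, so I use this probability only as an index of information.

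**Step 1: the any-AE contrast near the ceiling, 60 per arm.** Suppose Arm B is 60/60.
- Arm A 57/60: p = 117/120 = 0.975; z = 0.05 / sqrt(0.975 × 0.025 × 0.03361) = 1.75. Interval includes zero.
- Arm A 56/60: p = 116/120 = 0.967; z = 0.0667 / sqrt(0.967 × 0.0333 × 0.03361) = 2.03. Interval 0.4 to 16.0 points.

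So Arm A must fall to 56/60 (93%) or lower before the interval excludes zero. An observed 60/60 vs 59/60 gives 1.7 points (95% CI −4.4 to 8.9).

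| Assumed any-AE rates (A vs B) | Excludes zero, 60 per arm | 30 per arm |
|---|---|---|
| 97% vs 99% | 6% | 1% |
| 95% vs 98% | 12% | 3% |
| 95% vs 99% | 20% | 5% |
| 80% vs 95% | 73% | 45% |

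The item is uninformative only if the rates really are near the ceiling.

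**Step 2: the other two planned contrasts.**

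| Assumed DLT or discontinuation rates | 60 per arm | 30 per arm |
|---|---|---|
| 5% vs 20% | 73% | 45% |
| 10% vs 30% | 79% | 50% |
| 10% vs 25% | 58% | 34% |
| 10% vs 20% | 33% | 19% |

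These can separate the doses. The DLT-evaluable set may be smaller than 60, so the DLT figures are upper values.

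**Step 3: what each contrast can see after Cycle 1.**
- DLT: the window is Day 1 to Day 21 (5.1.3), so nothing later counts. Grade 3 neutropenia without fever meets none of the listed hematologic criteria.
- Discontinuation: Table 3 handles Grade 4 ANC, febrile neutropenia and other DLT-type events first by a hold and a reduced navarixin dose. A participant managed this way does not count. When ANC does not recover, navarixin stops and pembrolizumab continues; the plan does not say whether that counts as discontinuing study treatment.
- Any AE: counts the participant, but equally with one who had a single mild event.

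Severe toxicity after Cycle 1 that is managed without discontinuation therefore reaches only the any-AE contrast.

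**Step 4: a graded contrast.** With 27/60 vs 15/60, p = 42/120 = 0.35 and z = 0.20 / sqrt(0.35 × 0.65 × 0.03361) = 2.29. The difference is 20 points (95% CI 2.9 to 36.1). For assumed Grade 3-5 rates of 25% vs 45%, the interval excludes zero 63% of the time at 60 per arm and 36% at 30 per arm; for 25% vs 50%, 81% and 52%.

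Step 4 assumes a difference of 20 to 25 points and the first three rows of Step 1 one of 2 to 4 points, so they are not like for like: 25% vs 27% would exclude zero only about 5.5% of the time. The comparison shows that the graded endpoint has room to move and the ceiling endpoint does not.

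**The case against.** The strongest reply is that the plan does not depend on the any-AE item. A reader might infer that the primary safety comparison as a whole cannot separate 30 mg from 100 mg. The documents do not support that: DLT and discontinuation belong to the same primary endpoint, are contrasted by the same method, and discriminate reasonably (Step 2). A reader might also infer that neutropenia has no contrast. That is wrong too. Section 10.4.2 places Grade 4 ANC decrease within DLT, febrile neutropenia is a listed DLT criterion in 5.1.3, and ANC is summarized by arm and visit (10.6.3.2). Both points stand.

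It also stands that a near-100% AE rate is assumed, that no formal test is planned, that tolerability is decided within each arm by the DLT rule, and that AE counts by arm and clinical review of SAEs will be available.

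A further reply is that Section 10.6 leaves the comparison of the arms to the supplemental SAP. A graded contrast may be planned there, and I cannot rule it out. But safety is a primary objective, Section 10 is where primary analyses are set, and 10.6.2 already fixes the between-arm safety contrasts. A graded contrast belongs beside them.

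**Conclusion.** The concern holds in a limited form. The AE contrast in 10.6.2 is any grade and any cause. If AE rates are about 95% or higher in both arms, it carries little information on dose: about 6% to 20% probability of excluding zero for differences of 2 to 4 points at 60 per arm, and 5% or less at 30 per arm. At 80% vs 95% it would discriminate. The DLT and discontinuation contrasts are useful but leave a gap: no contrast uses grade after Cycle 1, although 5.4.1.2 says grades will be quantified. All rates here are assumed. No stopping or dose rule rests on this interval, so this is an inexpensive improvement to the safety analysis and not a flaw that undermines the trial.

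A separate inconsistency affects the DLT contrast. Section 10.4.2 counts Grade 4 ANC decrease as a DLT without a duration, while 5.1.3 requires Grade 4 hematologic toxicity of this kind to last at least 7 days. The two passages must be reconciled.

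**What to change.** In 10.1, 10.4.2 and 10.6.2, keep the three existing contrasts and add Miettinen-Nurminen differences with 95% intervals, over the whole treatment period, for participants with:
- at least 1 Grade 3-5 AE;
- at least 1 drug-related Grade 3-5 AE;
- Grade 3 or higher neutrophil count decrease.

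State in 10.6.2 whether stopping navarixin alone counts as discontinuing study treatment, and reconcile 10.4.2 with 5.1.3 on Grade 4 ANC decrease.

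The cost is SAP wording and three table rows. Appendix 4 already requires grade and causality for every AE, and hematology is drawn every cycle, so no new data are needed. The downside is three more unadjusted intervals in a trial with no multiplicity control; they should be labelled as estimates. If the arms stop at 30 each, these intervals will also be wide.

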### 10.6.3 Summaries of Baseline Characteristics, Demographics, and Other Analyses

### 10.6.3.1 Demographic and Baseline Characteristics

Demographic variables and baseline characteristics will be summarized.

#### 10.6.3.2 Pharmacokinetic and Pharmacodynamic Modeling Analysis

Pharmacokinetic parameters of study medicines will be summarized by planned visit and time for each arm separately.

ANC and percent change from baseline in ANC will be summarized by planned visit and time for each arm separately.

Pharmacokinetics and pharmacodynamics modeling analyses will be documented in the sSAP.

#### 10.7 Interim Analyses

There is one planned interim safety analysis and one planned interim futility analysis in this trial.

An interim safety analysis is planned for each arm after the first 10 participants across tumor types have finished at least one cycle of therapy in a given arm. If no more than 3 participants in the first 10 participants have experienced DTLs during the first cycle in a given arm, this arm may be expanded by enrolling 20 additional participants to complete Stage 1. Otherwise, this arm may be terminated due to safety concern.

An interim futility analysis is planned for each tumor type in each arm after the first 10 participants in each tumor type have at least 1 post-baseline scan assessment. If 1 or more

responses (ie,  $\geq 10\%$  response rate) are observed in a tumor type within an arm, this tumor type may be expanded to enroll at least 10 additional participants in Stage 2. Otherwise, this tumor type may be stopped early for futility. If the true response rate is 16%, there is an 82% chance to continue the study at the futility evaluation. If the true response rate is 20%, there is an 89% chance to continue the study at the futility evaluation.

Additional interim analysis may be conducted to enable future trial planning at the Sponsor's discretion and data will be examined on a continuous basis to allow for timely decisions.

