The overall design is an adaptive 2-stage design. In each arm, up to 30 participants will be enrolled in the first stage, and up to 30 participants in the second stage. In the first stage, 30 participants (with 10 per tumor type) will be enrolled in each arm (dose level). When all participants in a given arm with a given tumor type complete the first on-treatment scan at 9 weeks or when clinically indicated (see Section 9.2.1.2), a futility analysis will be conducted to determine whether that tumor type and arm will progress to Stage 2. If a tumor type passes the futility analysis (see Section 5.1.4) in Stage 1, at least 10 participants will be enrolled with that tumor type in the second stage.

Initial enrollment in each dose arm will be staggered. The first 3 participants in dose Arm A or dose Arm B will be enrolled no more frequently than 1 participant per week, to allow for peripheral neutrophil assessment between participants. Peripheral neutrophil assessment (ANC) will occur at baseline, Day 3, and Day 8 during the first cycle for all participants. Decreased ANC counts typically return to normal in 48-96 hours following dosing cessation. Standard support for oncology patients with low ANC will be considered as appropriate. See dose reduction algorithm (Section 7.2.1) for more information.

Specific procedures to be performed during the study, as well as their prescribed times and associated visit windows, are outlined in the Study SoA - Section 2. Details of each procedure are provided in Section 9 – Study Assessments and Procedures.

04W5XD

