#### **Futility Analysis** 5.1.4

An interim futility analysis for efficacy will be performed after the first 10 participants for each tumor type have at least 1 post-baseline scan assessment in each dose arm in Stage 1. If one or more responses (confirmed or unconfirmed) are observed for a tumor type in an arm (i.e.  $\geq$ 10% response rate), this tumor type may be expanded to enroll at least additional 10 participants in Stage 2, for a maximum enrollment of 60 participants in this arm across 3 tumor types. Otherwise, this tumor type may be stopped early for futility.

If the decision is made to expand a tumor type in dose Arm A to Stage 2, this tumor type in dose Arm B may be expanded to Stage 2 as well, irrespective of the number of responses as long as it has passed the safety evaluation. While the decision rule is mainly based on confirmed and unconfirmed responses, the totality of data will also be taken into account.

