#### **Number of Participants** 5.2

Greater than or equal to 120 participants will be randomized in order to achieve 120 evaluable participants as per Section 10. If no efficacy is noted in any tumor types the total number may be as low as 60.

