### 9.2.1.2 Tumor Imaging During the Study

The first on-study imaging assessment should be performed at 9 weeks ( $\pm 7$  days) from the date of randomization. Subsequent tumor imaging should be performed every 9 weeks ( $\pm 7$  days) or more frequently if clinically indicated. Imaging timing should follow calendar days and should not be adjusted for delays in cycle starts. Imaging should continue to be performed until disease progression is identified by the Investigator or the start of new anticancer treatment, withdrawal of consent, or death, whichever occurs first. All supplemental imaging must be submitted to the central imaging vendor.

Objective response should be confirmed by a repeat imaging assessment. Tumor imaging to confirm PR or CR should be performed at least 4 weeks after the first indication of a response is observed. Participants will then return to regular scheduled imaging, starting with the next scheduled imaging time point. Participants who receive additional imaging for confirmation do not need to undergo the next scheduled tumor imaging if it is less than 4 weeks later; tumor imaging may resume at the subsequent scheduled imaging time point. Note: Response does not typically need to be verified in real time by the central imaging vendor.

Per iRECIST (Section 9.2.1.5), disease progression should be confirmed by the site 4 to 8 weeks after first radiologic evidence of PD in clinically stable participants. Participants who have unconfirmed disease progression may continue on treatment at the discretion of the Investigator until progression is confirmed by the site, provided they have met the conditions detailed in Section 9.2.1.5. Participants who receive confirmatory imaging do not need to undergo the next scheduled tumor imaging if it is less than 4 weeks later; tumor imaging may resume at the subsequent scheduled imaging time point, if clinically stable. Participants who have confirmed disease progression by iRECIST, as assessed by the site, will discontinue study treatment. Exceptions are detailed in Section 9.2.1.5

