#### 10.4 Analysis Endpoints

### 10.4.1 Efficacy/Pharmacokinetics/Pharmacodynamic Endpoints

ORR as assessed by the investigator based on RECIST 1.1 is the primary endpoint. ORR as assessed by the investigator based on iRECIST, PFS as assessed by investigator based on RECIST 1.1 and iRECIST and OS are the secondary endpoints in this study. A description of efficacy measures is provided in Section 9.2 – Efficacy Assessments.

Objective Response rate (ORR) is defined as the proportion of participants who achieve a confirmed complete response (CR) or partial response (PR).

Progression-free Survival (PFS) is defined as the time from the first dose of study medication to the first documented disease progression or death due to any cause, whichever occurs first.

Overall survival (OS) is defined as the time from the first dose of study medication to death due to any cause.

Pharmacokinetic endpoints include serum concentrations of navarixin and pembrolizumab, as well as derived PK parameters.

Pharmacodynamic endpoint includes ANC.

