### 10.9 Sample Size and Power Calculations

For the planning purpose, it is assumed that true objective response rates of <1% for MSS CRC and 5% for PDL1-refractory NCSLC and advanced prostate are not considered clinically meaningful, whereas true objective response rates of 16% for MSS CRC and 20% for PDL1-refractory NCSLC and advanced prostate or higher are. With 20 participants in each tumor type of each arm under the 2-stage adaptive design, the probability that the objective response rate of each tumor type is claimed clinical meaningful is less than 8% when the true response rate is not clinically meaningful and more than 75% when the true response rate is clinically meaningful. The total sample size is 60 participants per arm (20 per each tumor type in an arm). No formal hypothesis testing will be conducted. Table 8 provides the probability that the objective response rate of each tumor type is claimed clinical meaningful under different true ORR. Table 9 shows the hypothetical ORR estimates and the CI (Clopper-Pearson interval) based on sample size of 20 per tumor type. Due to a small sample size, even an observed response rate as high as 30% (6 out of 20) could be coming from a true signal as low as 14%. A higher observed responses rate such as 8 out of 20 would be more indicative of a true response rate above 20%.

Probability That ORR is Claimed as Clinical Interest With 20 Participants in Each Table 8 Tumor Type of Each Arm

Tumor Type	ORR as clinical meaningful	True ORR	Minimum Responses that ORR is claimed as clinical meaningful	Probability that ORR is claimed as clinical meaningful
CRC	16%	1%	2	1%
		16%	2	77%
NSCLC,				
Prostate	20%	5%	3	7%
		20%	3	76%

The CI of the True ORR Under Different Hypothetical Number of Observed Response Scenarios With 20 Participants in Each Tumor Type of Each Arm

Hypothetical number of responses (CR or PR)	ORR	90% CI of ORR	80% CI of ORR
2	10%	(1.8%, 28.3%)	(2.7%, 24.5%)
3	15%	(4.2%, 34.4%)	(5.6%, 30.4%)
4	20%	(7.1%, 40.1%)	(9.0%, 36.1%)
5	25%	(10.4%, 45.6%)	(12.7%, 41.5%)
6	30%	(14.0%, 50.8%)	(16.6%, 46.7%)
7	35%	(17.7%, 55.8%)	(20.7%, 51.8%)
8	40%	(21.7%, 60.6%)	(24.9%, 56.7%)

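### Do the futility and Table 8 probabilities misdescribe the design because Section 10.7 leaves out parts of the Section 5.1.4 rule?

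*Combined protocol and SAP*

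**What the plan says.** Section 10.7 sets one futility look per tumor type in each arm, once the first 10 participants have at least one post-baseline scan. One or more responses allow expansion; otherwise the tumor type may be stopped. It then gives the chance of passing: "If the true response rate is 16%, there is an 82% chance to continue the study at the futility evaluation", and 89% at 20%. It does not say whether a response at the look must be confirmed.

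Section 5.1.4 has the same threshold and trigger and is more specific. It reads "If one or more responses (confirmed or unconfirmed) are observed for a tumor type in an arm", and it adds that, if a tumor type expands in Arm A, "this tumor type in dose Arm B may be expanded to Stage 2 as well, irrespective of the number of responses", provided Arm B has passed the safety evaluation. It also allows the totality of data to be weighed.

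The final endpoint is narrower. Section 10.4.1 states: "Objective Response rate (ORR) is defined as the proportion of participants who achieve a confirmed complete response (CR) or partial response (PR"). Section 9.2.1.2 sets the interval: "Tumor imaging to confirm PR or CR should be performed at least 4 weeks after the first indication of a response is observed".

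Section 10.9 claims, for 20 participants per tumor type per arm, a probability of declaring the response rate meaningful of less than 8% when it is not and "more than 75% when the true response rate is clinically meaningful". Table 8 gives 1% and 77% for CRC (true rates 1% and 16%), and 7% and 76% for NSCLC and prostate (5% and 20%). No formal test is planned.

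**The concern.** A reader of Section 10 alone would take these figures as properties of the rule used in both arms. Three things suggest otherwise.

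- The look can fall before any confirming scan, so a participant with a single post-baseline scan cannot yet be a confirmed responder. The rate seen at the gate need not equal the final confirmed rate on which Table 8 is built.
- The Arm B option can carry an arm with no responses into Stage 2, and Section 10 never mentions it.
- The look is worded in two ways. Section 5.1 waits until all participants of that tumor type and arm "complete the first on-treatment scan at 9 weeks or when clinically indicated"; Sections 5.1.4 and 10.7 refer to the first 10.

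The printed claim probabilities exceed 75% by only one or two points. With no formal test, they are the main quantitative support for the sample size.

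**Working it through.** **Inputs from the documents.** Stage 1 has 10 and Stage 2 a further 10 per tumor type per arm (Sections 5.1, 10.9). The gate is at least 1 of 10 (5.1.4, 10.7). A claim needs r = 2 of 20 for CRC and r = 3 of 20 for NSCLC and prostate, at the true rates p quoted above (Table 8). X1 and X2 are independent Bin(10, p) counts for the two stages.

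**Step 1: chance of passing.** P(pass) = 1 − (1 − p)^10.
- 16%: 1 − 0.1749 = 0.8251 (printed 82%; strict rounding gives 83%, which is immaterial).
- 20%: 1 − 0.1074 = 0.8926 (printed 89%).

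**Step 2: Table 8 with a binding gate in one arm.** Claim = P(Bin(20, p) ≥ r) − (1 − p)^10 × P(X2 ≥ r). The subtracted term is the loss from stopping after 0 of 10.
- CRC 16%: 0.8529 − 0.1749 × 0.4920 = 0.7668 (printed 77%).
- NSCLC/prostate 20%: 0.7939 − 0.1074 × 0.3222 = 0.7593 (76%).
- CRC 1%: 0.0169 − 0.9044 × 0.0043 = 0.0130 (1%).
- NSCLC/prostate 5%: 0.0755 − 0.5987 × 0.0115 = 0.0686 (7%).

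Without a gate the first two would be 85.3% and 79.4%, so Table 8 does assume a binding gate in each arm alone, with the same rate at the look and at the end.

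**Step 3: the Arm B option.** Suppose it is always used, Arm B passes safety, and the arms are independent. Let g be Arm A's chance of passing.

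Arm B continue = 1 − (1 − p)^10 × (1 − g). Arm B claim = Step 2 claim + (1 − p)^10 × g × P(X2 ≥ r).

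Example, CRC at 16% in both arms: continue = 1 − 0.1749² = 0.9694; claim = 0.7668 + 0.1749 × 0.8251 × 0.4920 = 0.8378.

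| Arm B case | CRC continue / claim | NSCLC/prostate continue / claim |
|---|---|---|
| Meaningful rate, own gate only | 82.5% / 76.7% | 89.3% / 75.9% |
| Meaningful rate, Arm A at the uninteresting rate | 84.2% / 77.5% | 93.6% / 77.3% |
| Meaningful rate in both arms | 96.9% / 83.8% | 98.8% / 79.0% |
| Uninteresting rate, own gate only | 9.6% / 1.3% | 40.1% / 6.9% |
| Uninteresting rate in both arms | 18.2% / 1.3% | 64.2% / 7.1% |

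The limiting case, in which Arm B always expands, gives false-claim probabilities of 1.7% and 7.5%. Arm A is unaffected throughout.

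**Step 4: response timing.** Let q be the share of eventual confirmed responders already visible at the look, and u the rate of never-confirmed responses among the others. **Neither is in the documents; both are assumptions.** For a single arm with a strict gate and x eventual responders in Stage 1, P(pass | x) = 1 − (1 − q)^x × (1 − u)^(10 − x), and the claim probability is the sum over x of P(X1 = x) × P(pass | x) × P(X2 ≥ r − x).

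| q | CRC, u = 0 | CRC, u = 5% | NSCLC/prostate, u = 0 | NSCLC/prostate, u = 5% |
|---|---|---|---|---|
| 1.0 | 76.7% | 80.1% | 75.9% | 77.3% |
| 0.9 | 73.6% | 78.2% | 74.0% | 76.1% |
| 0.8 | 69.9% | 75.8% | 71.3% | 74.4% |

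With u = 0 the 75% is lost below q of about 0.94 (CRC) or 0.95 (NSCLC/prostate). At q = 0.9, u of about 1.3% or 2.2% respectively brings it back to 75%.

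**The case for a change.** The strongest case for a change is that the probabilities sit in Sections 10.7 and 10.9 while the full rule sits in 5.1.4. At a true rate of 5% in both arms, an Arm B tumor type would enter Stage 2 with probability 64.2% rather than 40.1% if the option were always used, and Section 10 does not reveal this. Section 5.4.1.1 itself warns that responses to such agents can come late, so full visibility at week 9 is not a safe silent assumption.

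Part of this stands. Section 10 omits the Arm B option and the counting of unconfirmed responses, and nowhere says that Table 8 assumes a binding gate with the final response rate visible at the look. The margin over 75% is thin.

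The rest carries less weight:

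- Section 10 belongs to the same protocol as 5.1.4. The unqualified word in 10.7 does not contradict 5.1.4, which merely specifies it.
- The 82% and 89% need no assumption about confirmation. They hold for whatever response is counted, given its true rate. Only Table 8 links the look to the final confirmed count.
- Counting unconfirmed responses is how 5.1.4 deals with the four-week confirmation interval.
- The Arm B option is permissive and depends on safety. It can only raise Arm B's chances of continuing and of a claim, so the printed figures are its lower bound under Table 8's own assumptions.
- The wording of the look differs only if someone among the 10 lacks a scan. Section 5.2 ("Greater than or equal to 120 participants will be randomized in order to achieve 120 evaluable participants") and Section 6.5 on replacement do not define who counts at it.

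**Conclusion.** The concern does not call for a change. The printed probabilities are right for the per-arm rule that 10.7 states, and Table 8 is right for the same gate treated as binding. Both planning limits survive the Arm B option, with false claims at most 7.1% and true claims at 83.8% and 79.0% for equal rates. They also survive having no gate at all (7.5% at most; 85.3% and 79.4%).

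The one route below 75% needs incomplete visibility at week 9 with too few unconfirmed responses to offset it. The documents fix neither quantity, and the two work in opposite directions. Discretion to continue after 0 of 10 would offset the loss as well, although the permissive wording would equally allow a tumor type that passed not to be expanded. Computing a non-binding futility rule as though it were followed is ordinary practice in a phase 2 study without formal testing.

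What remains is missing detail that an analyst fills by reading 5.1.4 beside 10.7. Restating that rule in Section 10 would leave the gate, sample size, analysis and conclusions as they are. The Arm B figures assume independent arms, an option always used and safety passed; the timing figures are ranges under assumed q and u.
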